Phase	Phase II/III
Objectives	This study include three specific aims: Aim 1. To evaluate the short- and longer-term effectiveness of, PD alone ( PD ), PD + T-Wellness ( PDT ), and control (C, provision of child mental health and referral information). Hypotheses: (a) PD is more effective than control; and (b) PD with T-Wellness ( PDT ) is more effective for CHWs/teachers than PD alone; and (c) PDT has a more favorable cost-effectiveness ratio than PD alone; Aim 2. To examine effectiveness mechanisms and theory of change underlying the EBIs. Hypotheses: the mediational mechanisms of PD (teacher EBI strategy use as a mediator between intervention and child outcomes) and PDT (teacher stress management and EBI strategy use as mediators) will be supported; Aim 3. To examine implementation contextual factors and mechanisms that contribute to CHWs' (teachers') uptake and sustainment of EBI strategies within PD and PDT schools. Hypotheses: better fidelity, teacher mental health and more supportive contexts will be associated with better teacher uptake and sustainment of EBI strategies and more effective task-shifting.

Methodology	A cluster randomized controlled trial (cRCT), single blind and mixed-methods design will be applied. All study activities will be conducted in Uganda. Thirty-six public primary schools (18 urban and 18 rural), 540 teachers (~15 per school) and 1,980 parent-child pairs (~55 per school) will be recruited. Schools will be assigned to one of three conditions (PD, PDT, control). A stratified-block randomization procedure will be applied to ensure approximately similar characteristics across study regions and conditions.
Endpoint	Effectiveness outcomes will be assess 3 times (Time 1= before intervention; Time 2= immediate after PD/PDT intervention; Time 3= 12 months after Time 2). The primary teacher effectiveness outcomes (or intermediate effectiveness outcomes) are teachers' EBI strategy use and teacher stress management. The primary child effectiveness outcomes are child externalizing and internalizing problems (mental health outcomes). The secondary child effectiveness outcomes are emotion regulation, executive functioning (ability for cognitive processes that are foundation for the cognitive control of behavior), and social relationship (student-teacher relationship, peer relationship).

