## 1.2 **Rationale**

This study involves efforts to advance the science of prevention in early childhood mental health in low-resource communities. We will investigate the effectiveness, practical implementation strategies, and underlying mechanisms of the *PD* in urban and rural Uganda. We will compare effectiveness of two *PD* implementation approaches (with and without T-Wellness) using a hybrid effectiveness-implementation CRCT. **Figure 3** shows the conceptual model for *PD* and *PDT* Theory of change in LMIC contexts, which considers *intermediate intervention effectiveness outcomes* (teacher EBI practice) and *distal effectiveness outcomes* (including primary child mental health outcomes and secondary child behavioral outcomes, defined in Table 2). *PD* is expected to change teachers' EBI practices; and the impact of *PD* on distal child mental health outcomes will be mediated primarily through changes in teachers' practice of EBI strategies. Similarly, we expect that *PDT (PD+T-Wellness)* will also have impact on distal child mental health outcomes, and this will be mediated primarily through improvement in both teachers' EBI practices/behaviors and teachers' stress management skills (cognitive and behavioral control/ coping of stress). We anticipate *changes in child behaviors will be observed in the secondary outcome domains before the mental health outcomes* (primary distal outcomes). Because *PD/PDT* will be implemented in diverse contexts, our theory of change also considers moderators from aspects of the Consolidated Framework for Implementation Research (CFIR), which proposes that five domains of contextual factors can impact effectiveness-implementation. Specifically, we expect that certain *individual, intervention implementation, and school contexts* may also influence (or moderate) intervention effectiveness. We consider geographic region (urban/ rural) as the primary moderator, and other CFIR factors listed in the figure as secondary moderators. This theory of change has been partially tested (constructs in 'red' in Figure 3) and supported in previous *PD* studies. This study will formally examine the cost-effectiveness and test the *PD/PTD* theory of change with a larger diverse sample and using scalable approaches. We select a foreign low-resource country as our study site because it provides an ideal setting to test how a mental health system can be strengthened through careful consideration of strategies while simultaneously examining effectiveness outcomes of an EBI. Also, Ugandan context is similar to other underserved and under-resourced communities in the US and other LMICs. Therefore, knowledge generated from our study will be relevant globally.

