### **Aim 3. To examine implementation contextual factors and mechanisms that contribute to CHWs' (teachers') uptake and sustainment of EBI strategies within PD and PDT schools**

#### **2.1 Primary Objective**

The primary teacher effectiveness outcomes (or intermediate effectiveness outcomes) are teachers' EBI strategy use, teacher stress management. The primary child effectiveness outcome is child mental health (externalizing and internalizing problems)

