For effectiveness, intervention theory of change (mediation mechanisms), and cost-benefit evaluations, the child and teacher effectiveness outcomes will be assessed and evaluated across 3 time points- baseline (**T1**, before PD), immediately after the PD/PTD (**T2**, about 3-4 months after T1), and 12 months later (**T3**, about 18 months after T1). Data from **multiple sources** will be collected. For child effectiveness outcomes, the primary outcome is mental health (externalizing and internalizing problems), and the secondary outcome is behavioral and cognitive domains (see Table 2 for measures). Parent and child report data will be used. Parents of target students will be interviewed by trained research staff (using English or Luganda, lasting 30-45 minutes). Child assessment will be carried out in school by research staff (lasting about 20-30 mins). For teacher effectiveness outcomes, the primary teacher outcome is EBI practice, which will be based on objective observation by an independent observation team (primary data source) and teacher-report (secondary data source). The observation measure has been validated and published in our previous trial study (see [name] KY, [name] J, et al. Transportability of an Evidence-based Early Childhood Intervention in a Low-Income African Country: Results of a Cluster Randomized Controlled Implementation Study. *Prevention Science*. 2017;18:964-75). The secondary teacher outcome will be social process (i.e., teacher-student and teacher-family relationship), based on parent and child report. All primary outcomes and most secondary outcome measures have been used and validated in our previous Ugandan studies (see Table 2 for measures and reliability information from our Ugandan studies). Costs will be measured using an activity-based micro-costing approach in the intervention cluster (school), and in the extended implementation phase in all clusters from 6 through 12 months (n=36 clusters). Costs of the intervention will include all program costs incurred (for *PD/PDT* training, coaching, and materials/resources). Research costs will be excluded. Cost data collection will utilize existing standardized cost extraction forms and procedures that have been validated from Co-I [name]’s work in Uganda and LMICs. Prior to use, these tools will be tailored and customized. **Research staff for family and observation data collection will be masked** to intervention conditions. To ensure masking, we will have an independent assessment team (led by a separate research coordinator), and members will not participate in any intervention activities. We will also train implementation team on protocol to prevent releasing assigned condition information. Teacher-report data collection will not be masked. The tablet and team approach of data collection that we used in our previous studies will be applied.

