**Table 2. Key Study Measures for Effectiveness-Implementation Study: Constructs and Measures**

Dimensions	Constructs & Data Sources	Measures
Child Effectiveness Outcomes (T1-T3)	a) Mental Health (Primary): Externalizing & Internalizing b) RDoC domains (Secondary): Negative valence (emotion disregulation), social processes (student-teacher & peer relationship); cognitive system (executive functioning)	a) Strengths & Difficulties Questionnaire ( $\alpha=.63-.80$ )  (P); b) Emotion-regulation ( $\alpha=.90$ )  (P); Relationship with Teachers (C) ( $\alpha=.78$ )  & Peer relationship (P) ( $\alpha=.75$ )  ; Comprehensive Computerized Battery for Child Psychological Assessment (C) (for cognitive system, executive functioning) 
Teacher Effectiveness Outcomes (T1-T3)	a) Teacher EBI Practice (Primary): EBI Practices (including a range of behavior management and social emotional promotion practices (T & O); b) Teacher Stress & Management (Primary for PDT) (T) c) Teacher social process (secondary)- relationship (P)	a) Teacher EBI Practices: Classroom Observation (O) ( $\alpha=.68-.72$ )  ; PD Strategies Practice Questionnaire (T) ( $\alpha=.69-.80$ )  ; Determinants of Implementation Behavior Questionnaire (DIBQ)  b) Teacher Stress: Stress Questionnaire (T)  ; Stress Management: Irrational Belief Questionnaire  ; Responses to Stress Questionnaire  c) Family and Teacher Relationship Quality (P) 

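### The sections conflict on the primary teacher outcome for Aim 1 hypothesis (b), PDT versus PD, and no lead stress score or multiplicity rule settles which result counts

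*Combined protocol and SAP*

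**What the plan says.** Four places define the teacher outcomes.

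- **Protocol Summary, Endpoint.** The primary teacher outcomes "are teachers' EBI strategy use and teacher stress management". No arm is singled out.
- **Section 2.1.** The primary teacher outcomes are again "EBI strategy use, teacher stress management", with no arm restriction.
- **Section 6.1, prose.** "For teacher effectiveness outcomes, the primary teacher outcome is EBI practice, which will be based on objective observation by an independent observation team". Teacher report is the secondary source for that outcome. Then: "The secondary teacher outcome will be social process". Stress is in neither class.
- **Table 2 (in Section 6.1).** EBI practice is primary, and so is "Teacher Stress & Management (Primary for PDT) (T", the final letter being the teacher-report tag. The Stress Questionnaire is listed under stress. The Irrational Belief Questionnaire and the Responses to Stress Questionnaire are listed under stress management. No lead tool, subscale or composite is named. The note to the table makes classroom observation and teacher report both primary sources for teacher outcomes.

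Section 6.1 also states that collection of teacher-report data is not masked. Section 1.2 gives teacher EBI practice as the intermediate outcome, but expects PDT to work through EBI practice and "teachers' stress management skills (cognitive and behavioral control/ coping of stress".

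Hypothesis (b) of Aim 1 (Protocol Summary and Section 2) names no outcome, instrument or time point. Section 9 plans three pairwise contrasts, models T2 and then T2 to T3, and writes its model for students. It states no significance level, ordering of outcomes or multiplicity adjustment.

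**The concern.** Hypothesis (b) is the only hypothesis that tests whether T-Wellness adds effectiveness to PD. Under the Section 6.1 prose it would rest on masked classroom observation. Under Table 2 it could rest on any of several unmasked self-report scores that measure different things: stress level, beliefs, and responses to stress. A reader of the final report could not tell whether the score presented as primary was chosen before or after the results were seen.

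The choice carries forward. The Aim 2 plan in Section 9 restricts mediation testing to intermediate outcomes that improved significantly, so the score that happens to reach significance also decides what enters the PDT mediation model. The cost-effectiveness plan computes cost per SD change for each effectiveness outcome, so hypothesis (c) inherits the same ambiguity.

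**Working it through.** The documents give no significance level, power or sample-size figure for any teacher outcome, so there is nothing of the plan's own to reproduce. The check sets the statements side by side and then sizes the latitude.

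**1. Status of each outcome**

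| Place | Stress management | EBI practice by teacher report |
|---|---|---|
| Protocol Summary | Primary, no restriction | Source not given |
| Section 2.1 | Primary, no restriction | Source not given |
| Section 6.1 prose | Not listed | Secondary source |
| Table 2 and note | Primary for PDT | Primary source |

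These cannot all stand, and nothing in Section 9 says which governs.

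**2. Number of candidate stress scores.** There are two if only the tools labelled stress management count, and three if Table 2's wider heading, which takes in stress itself, is used.

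**3. Chance of a false favourable PDT-versus-PD result.** Assumptions: two-sided 0.05 per test (0.025 in the favourable direction), one time point, no true difference. For k independent scores the chance is 1 − 0.975^k.

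- k = 1: 2.5%
- k = 2: 1 − 0.975² = 4.9%
- k = 3: 1 − 0.975³ = 7.3%

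With three equally correlated scores (1,000,000 simulated draws) it is 6.3% at correlation 0.5 and 4.2% at 0.9.

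**4. Wider counts.** Adding observed practice and one teacher-reported practice score gives five: 1 − 0.975⁵ = 11.9% if independent, and 9.2% at correlation 0.5. Using both T2 and T3 raises the rate again. For three stress scores at two time points, the two-sided chance of any significant result is 18% to 24% for between-tool correlations of 0.7 to 0.3 and between-time correlations of 0.7 to 0.5. That figure counts both directions, so it is not comparable with those above.

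**5. Price of adjusting.** The documents give 12 schools per arm and about 15 teachers per school. Assume 80% power, no baseline adjustment, no loss, and a score from every teacher. Detectable d = (z for alpha + 0.842) × √[2(1 + 14 × ICC)/(12 × 15)], by normal approximation.

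- ICC 0.05 (assumed): √(2 × 1.70/180) = 0.137. At alpha 0.05, 2.802 × 0.137 gives 0.385. At 0.025, 3.083 × 0.137 gives 0.424. At 0.0167, 3.236 × 0.137 gives 0.445.
- ICC 0.10 (assumed): √(2 × 2.40/180) = 0.163. The same three levels give 0.457, 0.503 and 0.528.

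The levels 0.025 and 0.0167 are the strictest Holm steps for two and three primary results.

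**The case against.** The best defence is that the texts can be read together: EBI practice is common to both interventions, and stress management is added where T-Wellness is tested. Table 2 says primary for PDT, not primary only for PDT, and the Section 6.1 prose refers the reader to that table. This is a sensible intention, but the documents never state it, and the prose lists a secondary teacher outcome while leaving stress out altogether. Even on this reading no score or time point is named.

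Several stronger readings are tempting and should not be drawn.

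- **That stress management is declared primary for all arms.** The Protocol Summary and Section 2.1 merely state no restriction.
- **That Section 6.1 omits stress.** Only its prose does. The section disagrees with its own table.
- **That the false-positive risk is 11% to 14%.** Those are two-sided figures for three scores, and they include results in which PDT looks worse. The harm at issue is a false claim of benefit, for which about 5% to 7% is the relevant size.
- **That the belief scale merely tests what the PDT workshop teaches.** Section 4.5 says T-Wellness draws on strategies against irrational beliefs, so this is possible. But no item of the scale is shown, Box 1 does not name irrational beliefs among its topics, and Year 1 results will decide which components are kept. Coping is taught too, so the same suspicion would touch the other tool.

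It is also fair to say that the choice of tool belongs to the sponsor. The cognitive part of the Section 1.2 definition could point towards beliefs, and Table 2 gives no reliability value for any of the three stress instruments.

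**Conclusion.** The conflict holds and is worth correcting before outcome data are examined. It is more than missing detail, because different sections give different primary endpoints for the only test of what T-Wellness adds. The size is moderate: a false favourable claim has up to a 4.9% chance with two stress-management scores and 7.3% with three (6.3% at correlation 0.5), against 2.5% for one pre-named score. These rates rest on an assumed alpha, assumed correlations and a single time point; the contradiction rests on none of them. Bias from unmasked self-report would come on top and cannot be sized from the documents. They do not support a claim that any one instrument is invalid, or that selective reporting is intended.

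**What to change.** Put one statement in the Protocol Summary, Section 2.1, the Section 6.1 prose, Table 2 and its note:

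1. Masked observed EBI practice is a primary teacher outcome for every contrast, including PDT versus PD. Teacher-reported practice is secondary.
2. Stress management is an additional primary outcome for the contrasts involving PDT, on one pre-named score at one pre-named time point. The Responses to Stress Questionnaire is a reasonable candidate given the Section 1.2 definition, provided the exact score is specified. The sponsor may justify another, or keep both stress-management tools with a Holm adjustment.
3. The Stress Questionnaire and any tool not chosen are secondary.
4. Hypothesis (b) states whether it needs both primary outcomes or either one, with Holm adjustment if either suffices.
5. The text acknowledges that the stress score is unmasked self-report.

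The instruments are already planned, so no data collection is added. The costs are that a favourable result on an unchosen score no longer counts as primary success, and that adjustment takes some power: at the strictest Holm step for two outcomes, the detectable d rises from about 0.39 to 0.42 at ICC 0.05, or from 0.46 to 0.50 at ICC 0.10. Under Section 11.2 the amendment needs approval from both IRBs.

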**Table 2. Key Study Measures for Effectiveness-Implementation Study: Constructs and Measures**

Dimensions	Constructs & Data Sources	Measures
Child Effectiveness Outcomes (T1-T3)	a) Mental Health (Primary): Externalizing & Internalizing b) RDoC domains (Secondary): Negative valence (emotion disregulation), social processes (student-teacher & peer relationship); cognitive system (executive functioning)	a) Strengths & Difficulties Questionnaire ( $\alpha=.63-.80$ )  (P); b) Emotion-regulation ( $\alpha=.90$ )  (P); Relationship with Teachers (C) ( $\alpha=.78$ )  & Peer relationship (P) ( $\alpha=.75$ )  ; Comprehensive Computerized Battery for Child Psychological Assessment (C) (for cognitive system, executive functioning) 
Teacher Effectiveness Outcomes (T1-T3)	a) Teacher EBI Practice (Primary): EBI Practices (including a range of behavior management and social emotional promotion practices (T & O); b) Teacher Stress & Management (Primary for PDT) (T) c) Teacher social process (secondary)- relationship (P)	a) Teacher EBI Practices: Classroom Observation (O) ( $\alpha=.68-.72$ )  ; PD Strategies Practice Questionnaire (T) ( $\alpha=.69-.80$ )  ; Determinants of Implementation Behavior Questionnaire (DIBQ)  b) Teacher Stress: Stress Questionnaire (T)  ; Stress Management: Irrational Belief Questionnaire  ; Responses to Stress Questionnaire  c) Family and Teacher Relationship Quality (P) 
Contextual Moderators (Pre/T1 and Post PD training, and during PD implementation)	a) Outer setting: Urban/rural region (Primary moderator) b) Fidelity: 4 PD/PDT measures (F, T) c) Inner setting: School EBI climate (e.g., work environment, team work alliance, leadership) (T); d) Individual/Teacher characteristics (e.g., EBI readiness/attitude; wellness) (T) e) Intervention characteristics: Acceptability; Appropriateness (T) f) Processes: Partnership Quality (e.g., TTC and teacher/PTA partnership) (T)	b) 4 Fidelity measures  (1) Adherence (F) (deliver the core content): PD/PDT Fidelity Checklists (completed after each training day & coaching session) (2) Quality of implementation (T) (Teacher Satisfaction (T) (post PD training and T2) ( $\alpha=.72$ )  and ratings of Coaches' competence); (3) Engagement (T) Strategy Knowledge  (T) (EBI knowledge gain before-after training) (test-retest $r=.35-.43$ )  ; (4) Exposure (F): Attendance tracking  ; C) School Environment Survey  ; Organization Climate Questionnaire ( $\alpha=.65-.85$ )  d) Teacher demographic  ; PHQ-mental health  ; EBP Attitude Scale  ; e) Applied Mental Health Research Dissemination and Implementation Measurements (AMHRG)  ; f) Partnership Questionnaire 
Demo (T1)	Family/Student Demo (e.g., parenting, well-being) (P)	Family: Demo  ; Parent EBI Practices (P) ( $\alpha=.69-.80$ )  ; PHQ ( $\alpha=.90$ ) 
PD/PDT Cost	Program implementation costs;	Implementation costs: actual program costs (with & without monitoring cost) 

**Note.** For **child effectiveness outcomes**, primary data source is parent-report (P); and secondary data source is child-report/testing (C). For **teacher effectiveness outcomes**, primary data sources is classroom observation (O) & teacher report (T); and secondary data source is Parent (P) report. **CFIR contextual data** will be gathered from Training/coaching session tracking data from facilitator report (F) and teachers-report (T). **Suicidal behaviors** are NOT included because this study focuses on preventive intervention and young children (ages 4-10 years). The measures used in young children usually do not include suicidal items. However, parent, teacher, and child reported depressive symptoms will be included.

